### 11.4 Procedures for Dealing with Severe Adverse Events

In the event of any SAE which, in the investigator's opinion, justifies termination or modification of the trial (see [Section 7.5.2](#)), dosing will be stopped and the sponsor's medical monitor will be informed immediately (within 24 h of the investigator becoming aware of the event) by telephone or email, as follows.

[REDACTED] MD, MSc, PhD  
Tel: [REDACTED]

Email: [REDACTED]  
Mobile: [REDACTED]

For all SAEs, the investigator will complete a SAE form and provide it to the sponsor's pharmacovigilance department immediately (within 24 h of the investigator becoming aware of the event), as follows.

[REDACTED] MD, MSc, PhD  
Tel: [REDACTED]  
Email: [REDACTED]  
Mobile: [REDACTED]

The sponsor will also be notified by email [REDACTED]  
[REDACTED]

The investigator will notify the REC of SAEs that occur during this trial, if applicable, in accordance with the SOPs issued by the Research Ethics Service (RES).

The sponsor is responsible for determining the expectedness of the event, using the reference safety information in the Investigator's Brochure. The sponsor will notify the MHRA of all suspected unexpected serious adverse reactions (SUSARs), and will be responsible for ensuring that the REC is notified of SUSARs, if applicable.

SUSARs that are fatal or life-threatening must be notified to the MHRA and REC within 7 days after the sponsor has learned of them. Other SUSARs must be reported to the REC and MHRA within 15 days after the sponsor has learned of them.

## 11.5 Procedures for Handling Withdrawals Due to Adverse Events

The investigator will assess the reason for withdrawal as far as possible and will fully record the circumstances and medical details. Provided that subjects give written informed consent, they will undergo the standard medical examination and laboratory tests at withdrawal from the trial which they would have undergone had they completed it (see also [Section 7.6.1](#)).

## 11.6 Procedures for Reporting Pregnancies

Subjects will be asked to follow the contraception guidance in [Section 8.1](#).

If, during the study, the investigator becomes aware of a pregnancy in a subject, or a partner of a subject, they will inform the sponsor's pharmacovigilance department immediately (within 24 h of the investigator becoming aware of the event), as follows.

[REDACTED] MD, MSc, PhD  
Tel: [REDACTED]  
Email: [REDACTED]

Mobile: [REDACTED]

The investigator will follow-up the pregnancy according to [REDACTED] SOPs, provided the subject's partner consents to that. A pregnancy will not constitute an SAE unless it meets one of the criteria in Section 11.3.

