- Screening Assessments:** Screening will be within 21 days before imaging session 1.
- Imaging Admissions:** Admission for imaging session 2 will be within 7 days after the baseline PET scan; and admission for imaging session 3 will be within 7–14 days after imaging session 2.
- PET Repeat/Reschedule:** In the case of technical failures (i.e., such as unsuccessful tracer synthesis or a PET scanner malfunction etc.) a PET scan may need to be repeated or rescheduled. In such cases, subjects may be asked to stay for up to 48 h longer in each imaging session or repeat an imaging session at a later date. If the failure affects imaging session 1 before administration of radioactivity, the baseline scan may be repeated. If the failure affects imaging session 1 after administration of radioactivity, the baseline scan may be repeated once. If the technical failure affects imaging sessions 2 or 3 (after the subject has received an ASN51 dose), a third imaging session may be required, after a 7-day washout of the last dose of ASN51. Subjects will receive no more than 3 single doses of ASN51, or 3 doses of [F]-IMA601 during the study.
- Follow-up Visit or ET:** A follow up visit will be 7 days ( $\pm 3$  days) after the last on-treatment PET scan. Additional follow-up by telephone for any potential SAEs will be 28 days ( $\pm 3$  days) after the last on-treatment PET scan.
- Inpatient Stay:** Subjects will be admitted on Day -1 of imaging sessions 1, 2 and 3. Subjects will remain inpatient for both imaging sessions 2 and 3 for up to 72 h after dosing. In session 1, subject may leave the clinical unit in the evening of Day 1.
- MRI Questionnaire:** Subjects will complete an MRI questionnaire before the MRI scan, to exclude unsuitable subjects.

7. **MRI Scan:** Screening MRI will occur once all other screening results are available. If a subject is being re-screened (i.e. missed cohort) and there is already a recent MRI scan available within 3 months from their first screening period (ie if subjects were a reserve subject for a previous group but were not dosed and are no longer within the screening window) they do not need to have a repeat MRI scan.
8. **Venous cannulation:** One for administration of [F]-IMA601 (all imaging sessions) and one PK sampling (imaging sessions 2 and 3) (two venous cannulae be used).
9. **[F]-IMA601 Administration:** At the start of each PET scan.

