### 8.2 Inclusion/Exclusion Criteria

#### Inclusion Criteria:

Individuals meeting all the following **inclusion criteria** and none of the **exclusion criteria** will be eligible to participate. None of the inclusion criteria are eligible for re-screening. No waivers will be granted and any deviation from below will get recorded as a major protocol deviation. An exception can apply for subjects who meet the inclusion and exclusion criteria, but then miss a cohort that is filled and so they are no longer eligible due to lapse of the 3-week screening window; these subjects may be rescreened.

1. Healthy as determined by the Investigator, based on a medical evaluation including medical history physical examination, neurological examination, laboratory tests and cardiac monitoring.
2. Men or women aged 25-55 years, inclusive (age range was selected on grounds of radiation burden).
3. Women of child-bearing potential with partners of child-bearing potential (see [Section 9.10.7](#) for definitions) must agree to use highly effective contraception (per CTG 2020; bilateral tubal occlusion, hormonal contraception associated with inhibition of ovulation except oral contraception, intra-uterine device with or without intrauterine hormone-releasing system, sexual abstinence in relation to the preferred and usual lifestyle of the subject, ) from at least 28 days before first tracer dosing through 30 days after last dose of IMP. All women of child-bearing potential must have a negative pregnancy test result before administration of test article. Vasectomised partner is also an accepted a highly effective birth control method provided that partner is the sole sexual partner of the WOCBP trial participant and that the vasectomised partner has received medical assessment of the surgical success.
4. Women of non-childbearing potential must be postmenopausal [the last menstrual period was at least 12 months ago, and FSH at screening confirms postmenopausal status], or have no uterus, ovaries, or fallopian tubes). Women who are surgically sterile must provide documentation of the procedure by an operative report or by ultrasound.

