5. Non-sterilized male subjects who are not abstinent and intend to be sexually active with a female partner of childbearing potential must use a male condom plus spermicide from 1 day prior to the first tracer administration throughout the total duration of the treatment period and 90 days after the last dose of IMP. Periodic abstinence, the rhythm method, and the withdrawal method are not acceptable methods of contraception. Male subjects should refrain from sperm donation throughout this period.
6. Body weight > 50.0 kg for men and >45.0 kg for women and Body Mass Index within the range 18.5-30.0 kg/m^2 (inclusive).
7. Subjects must understand the nature of the study and must provide signed and dated written informed consent in accordance with local regulations before the conduct of any study-related procedures.
8. Subjects must be, in the opinion of the Investigator, able to participate in all scheduled evaluations, likely to complete all required tests, and likely to be compliant.
9. Subjects must be fluent in the local language.
10. Subjects must agree not to post any personal medical data related to the study or information related to the study on any website or social media site (e.g., Facebook, Twitter, etc.) until the trial has completed.

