#### **10.4.5 Pregnancy Testing**

A negative serum pregnancy test is required from WOCBP within 24 hours before the first dose of IMP. Additional serum pregnancy tests (or urine pregnancy tests for MRI visit at [REDACTED]) will be obtained from females (WOCBP) at all subsequent clinic visits as noted in the Schedule of Events (Table 1).

All pregnancy tests will be performed at the site's local laboratory [REDACTED]. Pregnancy in subject or partner must be reported ([Section 11.6](#)); pregnant subjects will be discontinued from the trial.

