## 11.0 ADVERSE EVENT DEFINITIONS, REPORTING, AND FOLLOW-UP

All AEs, SAEs, SARs, and pregnancies occurring during the protocol-specified timeframes ([Table 1](#)) will be assessed and reported per guidelines provided in the following sections.

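### Pregnancy reporting is not carried to the end of the protocol's own contraception windows; for partners of male subjects the last scheduled contact comes about two months before day 90

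*Protocol*

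**What the plan says.** **Reporting duty.** Three places in the protocol bear on it:

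- Section 11.6 requires notice to pharmacovigilance at the sponsor within 24 hours, in a sentence that begins: "If, during the study, the investigator becomes aware of a pregnancy in a subject, or a partner of a subject, they will inform".
- Section 11.0 covers "pregnancies occurring during the protocol-specified timeframes" and refers to Table 1 for those timeframes.
- Section 10.4.5: "Pregnancy in subject or partner must be reported". It gives no end date and points to Section 11.6.

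**Contraception windows (Section 8.2).** Women of child-bearing potential use highly effective contraception "from at least 28 days before first tracer dosing through 30 days after last dose of IMP" (inclusion criterion 3). Men use a condom with spermicide "throughout the total duration of the treatment period and 90 days after the last dose of IMP" (inclusion criterion 5).

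**Contacts after the last dose.** In Table 1 the last pregnancy test is at the follow-up visit, 7 (±3) days after the last on-treatment scan. After that there is one telephone call: "Additional follow-up by telephone for any potential SAEs will be 28 days" (±3) after the last on-treatment scan. Section 10.3.10 gives the call the same purpose and timing, four weeks after the last tracer dose. Section 7.4 instead shows six weeks for this telephone step.

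**Pregnancy and SAE status.** Section 11.6: "A pregnancy will not constitute an SAE unless it meets one of the criteria in Section 11.3".

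**The concern.** By setting the contraception periods, the protocol says how long it regards conception as a concern after ASN51. The reporting rule is not linked to those periods. It depends on when the investigator hears of the pregnancy, within a period that is not defined for this purpose.

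A partner pregnancy conceived, say, seven weeks after a man's last dose lies inside the protocol's own window. Yet the schedule has no later contact at which it would come up, and for the last subjects the written duty may already have ended. In a phase 1 study this is exposure information that is hard to recover if nobody asks. The stake is completeness of safety reporting; no endpoint or analysis depends on it.

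**Working it through.** All times are in days after the last ASN51 dose.

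**Inputs**
- Dose-to-scan lag: 0 to 2 days, since on-treatment scans may be scheduled up to 48 h after the dose (Section 7.1).
- Follow-up visit with the last pregnancy test: 7 ± 3 days after the last scan (Table 1 and its notes).
- Telephone call: 28 ± 3 days after the last scan (Table 1 notes).
- End of contraception: day 30 for women, day 90 for men (Section 8.2).
- End of trial: the last subject's protocol-specified visit or assessment (Section 7.7).

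**Formulas.** Contact day = lag + days from scan to contact. Remaining window = end of contraception − contact day.

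**Call**
- Earliest: 0 + 25 = 25. Latest: 2 + 31 = 33.
- Men: 90 − 33 = 57 to 90 − 25 = 65 days remain. At exactly 28 days after the scan, 90 − 30 = 60 to 90 − 28 = 62.
- Women: 30 − 33 = −3 to 30 − 25 = 5. The call falls between 5 days before and 3 days after the window closes.

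**Last pregnancy test**
- Earliest: 0 + 4 = 4. Latest: 2 + 10 = 12.
- Women: 30 − 12 = 18 to 30 − 4 = 26 days of the window follow the last test.

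**Sensitivity to Section 7.4.** The section does not say where its six weeks start. Its steps add as 3 + 3 + 6 = 12 weeks, so I assume they follow the follow-up visit.
- Call: 4 + 42 = 46 to 12 + 42 = 54.
- Men: 90 − 54 = 36 to 90 − 46 = 44 days remain.
- Women: day 30 has passed before the call.

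**Who is outside the duty, as opposed to after the last contact.** Suppose the study period in Section 11.6 means the whole trial, ending at the last subject's call. A man whose last dose came k days before the last subject's is then covered to day k + 25 to k + 33 after his own dose. Coverage reaches day 90 when k is at least 57 to 65. Men dosed earlier than that are inside the duty throughout, although nobody is scheduled to ask them. For the last man treated k is 0, so the full 57 to 65 days fall outside both.

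**Whether another section closes the gap.** Section 10.4.5 returns the reader to 11.6. Section 11.0 sends the reader to Table 1, where the pregnancy entries are tests ending at the follow-up visit. For contraception, 11.6 cites Section 8.1, which explains the use of healthy young volunteers; the contraception text is in 8.2. None of these supplies a reporting period to day 30 or day 90.

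**The case against.** The strongest case on the other side has five parts.

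- **Section 10.4.5 is unqualified.** It requires reporting for subjects and partners with no cut-off. This stands to the extent that the documents leave the period undefined; they do not forbid later reporting. But 10.4.5 defers to 11.6, which carries the limit.
- **The call may cover pregnancy.** A reader might infer that it asks about SAEs and nothing else. The text gives a purpose and does not exclude other questions. Nor does 11.6 say that a pregnancy can never be an SAE, since it makes an exception for one that meets a criterion. What stands is that nothing requires the question.
- **There is no real timing gap for women.** This is right. A reader might take the 18 to 26 days after the last test as unobserved, but the call falls at about day 30 and could ask.
- **Unseen sources may help.** Section 11.6 cites SOPs that are not available here, and the consent pages were removed before review. They could contain a longer period. As cited, though, the SOPs govern how a known pregnancy is followed up. Section 11.3 tells subjects to report adverse events after discharge, but pregnancy is not among the adverse event examples, and Sections 10.3.10 and 11.0 list it separately.
- **The stakes are small.** There are at most 10 healthy subjects, few single doses, required contraception and no affected endpoint. This limits the weight of the point, but the remedy is also small.

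**Conclusion.** The point holds, mainly for partners of male subjects and chiefly for the last men treated. No section carries pregnancy reporting to the end of the contraception windows. The last scheduled contact comes 57 to 65 days before the men's window closes, or 36 to 44 days before it on the assumed reading of Section 7.4. For women the defect is what the call is stated to cover, not when it happens.

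A reader might infer that about two-thirds of the 90 days lies outside the reporting duty for every male subject. The documents do not support that: the figure counts days after the last contact, and on a trial-wide reading men dosed early stay inside the duty for longer.

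The figures rest on the Table 1 visit windows and a dose-to-scan lag of up to 48 h. The conclusion also assumes that the unseen SOPs and consent text do not set a longer reporting period. This is a worthwhile low-cost improvement to safety reporting, with no bearing on any statistical result.

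**What to change.** 1. In Section 11.6, replace the limit to the study period with a duty to report any pregnancy conceived up to the end of the contraception windows in inclusion criteria 3 and 5, whenever the site learns of it. Dating by conception matters because a late conception is recognised only after the window closes. Align Sections 11.0 and 10.4.5 with this.
2. Add a pregnancy question, covering subject and partner, to the existing telephone call. This alone would miss recent and later conceptions, so step 3 is also needed.
3. At discharge, instruct subjects to report any pregnancy in themselves or a partner conceived within the window.
4. Reconcile the timing of the call (28 days in Table 1, four weeks in Section 10.3.10, six weeks in Section 7.4). Correct the Section 11.6 cross-reference from 8.1 to 8.2.

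The cost is protocol and consent wording plus one question in a call already planned, with no extra visit or test. The site must accept reports for about two months or more after the last call.

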## 11.7 Trial Conduct

This study will be conducted in compliance with the protocol approved by the Research Ethics Committee (REC) and the Medicines Healthcare and Products Regulatory Agency (MHRA), and according to Good Clinical Practice standards. No deviation from the protocol will be implemented without the prior review and approval of the REC/MHRA except where it may be necessary to eliminate an immediate hazard to a research subject. In such case, the deviation will be reported to the REC/MHRA as soon as possible.

## 12.0 STATISTICAL METHODS

The completeness of the data affects the integrity and accuracy of the final trial analysis. Therefore, every reasonable effort will be made to ensure complete, accurate, and timely data collection, and to avoid missing data. In general, missing data will be treated as missing and no statistical imputation method will be used unless stated otherwise. The procedures for handling missing, unused, or spurious data will be presented in the Statistical Analysis Plan (SAP).

### 12.1 Statistical Analysis Plan (SAP)

A SAP (and data management plan (DMP), if appropriate) will be written and finalized before the database closure. The SAP will provide full details of the analyses, the data displays and the algorithms to be used for data derivations.

The SAP will include the definition of major and minor protocol deviations/violations and the link of major protocol deviations/violations to the analysis sets.

Any deviations from the original statistical plan will be described and justified in the final report.

### 12.2 Analysis Populations

Three different analysis sets are defined. Subjects who withdraw from the study, or who have missing data, will be included in the statistical analyses provided that they are eligible for inclusion in the analysis population as described below.

**All-treated set:** This analysis set includes all randomized subjects who received study drug (at least one dose).

**Safety set:** This analysis set includes subjects from the all-treated set who had at least one safety assessment post-baseline. The safety set will be employed in the analysis of tolerability and safety variables.

**PET population:** The PET population will consist of randomised subjects who receive study medication, have a baseline PET scan, at least one post-baseline PET scan, and a PK result immediately preceding PET scan.

**PK analysis population:** The PK analysis population will consist of the subjects who provide evaluable data for the comparisons of interest. These subjects should have at least one quantifiable plasma concentration, should not have violated any major entry criterion likely to confound the PK analysis, and should not have deviated significantly from the protocol between enrolment and successful study completion

In all populations, treatment will be assigned based upon the treatment subjects actually received.

The primary endpoint will be analyzed using the PET population.

### 12.3 Sample Size

The trial is hypothesis generating, so no formal calculation of sample size is appropriate. The sample size of at most 10 subjects is considered adequate to allow modelling of the relationship between ASN51 plasma concentrations and the occupancy of O-GlcNAcase and is within the range generally accepted for PET studies. Enrolment of subjects into the study will be stopped as soon as the brain O-GlcNAcase occupancy versus ASN51 plasma concentrations is sufficiently characterized in opinion of the SRC.

### 12.4 Procedure for Accounting for Missing, Unused, and Spurious Data

All analyses will be performed on data available at the time point considered. In summary tables, the number of subjects with missing data will be presented unless otherwise specified. In calculation of percentages, subjects with missing data will not be considered in numerator or denominator unless otherwise specified.

### 12.5 Discontinuations

The number of subjects randomized who complete the treatment period (through each interim analysis time point) and who discontinue the trial will be summarized. Reasons for discontinuation will be summarized.

### 12.6 Pharmacokinetic Statistical Analysis

A definition of the PK parameters is described in [Section 10.5](#). PK parameters will be described descriptively.

The PK analysis population will be used for all PK analyses. Individual subject listings will be provided. Mean and individual plasma concentration-time profiles for ASN51 will be presented graphically for each group.

PK variables will be summarized using arithmetic mean, STD, geometric mean, median, minimum, maximum, and %CV and by means of scatterplots, dose-normalized scatterplots versus dose and means plots versus the dose.

## 12.7 Safety and Tolerability Parameters

Definitions of the safety and tolerability parameters are described in [Section 10.3](#). The safety set is used to perform all safety analyses.

The medical history is coded using the most recent MedDRA version and listed. All AEs and SAEs are coded using the most recent MedDRA version.

The treatment-emergent AEs are tabulated by system organ class (SOC), and individual preferred terms within each SOC by treatment group. The number and percentage of patients who experienced AEs coded with the same preferred term and SOC will be summarized by treatment group (in descending order according to the incidence in the investigational study drug group). Adverse events will also be tabulated by severity and by relationship to study drug. Summary tables will be accompanied by individual subject listings broken down by treatment group, including pre-dose events. Separate summary tables of adverse events for related/all AEs will be provided including severity and percentages.

SAEs will be listed and summarized similarly to AEs. Reasons for death will only be listed.

Reasons for premature discontinuation of study drug will be listed and summarized by frequency tables.

ECG variables, vital sign measurements and laboratory measurements will be summarized at each time point using mean, median, standard deviation, min, max, number of available observations, and change from baseline. Individual patient listings of ECG data, and laboratory measurements will be provided.

In addition, ECG parameters will be analyzed as follows (data listings):

- 450 ms < QTcF/ QTcB <= 480 ms
- 480 ms < QTcF/ QTcB <= 500 ms
- 500 ms < QTcF/ QTcB
- 30 ms < QTcF/ QTcB change from baseline <= 60 ms
- 60 ms < QTcF/ QTcB change from baseline

The mean +/- SD and median over time for ECGs will be plotted by line graphs. An analysis will be provided for the concentration versus ECG parameters based on a linear regression model (numerical and graphical analysis). The regression model will contain the change from baseline of

QT/QTcB/QTcF as the dependent variable and include the corresponding plasma concentrations of ASN51 (i.e., the plasma concentration taken at the closest timepoint to the ECG recording) as the independent variables and the subject as a random effect. Pre-dose and follow-up ECGs will not be included in this analysis.

Abnormal ECG observations will be listed.

Listings for each laboratory, ECG and vital sign parameter out of normal range will be provided, separately for above/below normal range per time point. Standard numeric laboratory parameters are presented in the units supplied. If needed, a conversion will be made to standard units.

